# 8.1.2 Within 5 Days Before Treatment

- Conduct medical history (including collection of AE reporting) and review of concomitant medications (including all transfusion requirements up to 28 days prior to dosing)
- Report human leukocyte antigen (HLA) typing if available
- Evaluate ECOG performance status
- Conduct physical examination (examination of skin, HEENT [head, eyes, ears, nose, throat], lymph nodes, heart, chest, lungs, abdomen, extremities, and neurologic system), including height, weight, and disease assessment
- Obtain ECG, standard 12-lead
- Take vital signs (including blood pressure, heart rate, respirations, pulse oximetry, and temperature)
- Obtain specimen for CBC with differential and platelet count
- Obtain specimen for chemistry panel (ALB, ALK-P, ALT, AST, BUN, HCO3, Ca, Cl, creatinine, glucose, K, Na, total bilirubin, total protein) and CRP
- Obtain specimen for Special Chemistry (phosphorus, uric acid, CK)
- Obtain specimen for coagulation studies (PT, aPTT)
- Obtain specimen for urinalysis and examination of urinary sediment
- Perform urine or serum β-hCG pregnancy test for women of childbearing potential
- Obtain peripheral blood for flow cytometric evaluation

# 8.1.2.1 Patient Registration

Each patient must be registered with MacroGenics before study entry. The following information should be provided during registration:

• AML diagnosis, including disease risk classification and cytogenetics

- Prior AML treatment history, including dates of treatment, outcome of treatment, best response, and treatment failure, as well as number of treatment cycles received and duration of prior treatment outcome.
- Date of signed informed consent
- Planned date of first drug administration
- Confirmation of conformity to the entry criteria

# 8.1.3 Within 1 Day Before Treatment

Initiate TLS prophylaxis for patients with AML employing hydration, allopurinol, and oral phosphate binders as defined by institutional practices and standard of care.

# 8.2 Study Evaluations Applicable During Cohort Expansion

Patients may be treated on an outpatient basis after Cycle 1 Day 8 (and after a minimum of 24 hours at the 500 ng/kg/day maximum dose) of study treatment guided by tolerability of the regimen during the first 8 days of dosing, and at the discretion of the Investigator. Cycles 2 and greater may be administered as an outpatient if the previous cycle was well-tolerated.

During Cycle 1, laboratory assessment samples are to be drawn around the same time each day, and prior to start of infusion or dose change as applicable and after end of infusion on days when infusions end unless otherwise indicated.

# 8.3 End of Treatment Visit/Follow-up

# 8.3.1 End of Treatment Visit: 28-Days (4 Weeks) After Last Dose of Study Drug or at the Time of Treatment Failure

It is recognized that certain patients (such as those experiencing progression of disease) may be cared for in facilities other than the participating investigational site, may proceed to receive other anti-leukemic therapy, and/or may elect not to return to the investigational site. Therefore, this visit is considered optional, but should be carried out whenever possible.

# 8.3.2 Follow-up Period

Follow-up information will be requested by the Sponsor after end of treatment until death or withdrawal of consent, but not beyond 2 years after the last patient is enrolled. All patients will have clinical information including safety, transfusion requirements, disease and vital status information collected during the follow-up period. Depending on treatment response, patients may be required to continue follow-up at the study site for the first 6 months post treatment. After these first 6 months, follow-up can be conducted outside of study site, but follow-up information must still be provided to Sponsor as outlined.

#### **Follow-up Frequency**

#### • Responders (CR, CRh, CRi [CRn, CRp], or MLFS):

Patients who respond to treatment should have monthly visits at the study site for 6 months post end of treatment. After 6 months post treatment, patients may be followed up at the study site or by a local physician, and follow-up data will be collected at 3-month intervals.

#### • Non-Responders:

Patients who do not respond to treatment may be followed up at the study site or by a local physician, and follow-up data will be collected at 3-month intervals post treatment.

#### **Bone Marrow Aspirate and Biopsy**

### • Responders (CR, CRh, CRi [CRn, CRp], or MLFS):

Patients who respond to treatment should have a bone marrow aspirate and biopsy collection at 3 and 6 months post treatment at the study site. After 6 months post treatment, bone marrow aspirate and/or biopsy will be performed per standard of care.

#### • Non-Responders:

Patients who do not respond to treatment will have bone marrow aspirate and/or biopsy performed per standard of care.

#### • All patients:

If patients have a bone marrow aspirate and/or biopsy done as part of their standard of care, they have the option to consent to donate aspirate or biopsy specimens for assessment of disease status and further research to help elucidate immune mechanisms involved in flotetuzumab function. As with all other biopsies collected for this study, these samples may be used for histopathological and immunohistochemical evaluation, flow cytometric evaluation, and minimal residual disease analysis.

#### **Disease and Vital Status**

The Sponsor will request the following clinical data that supports or gives context to the patient's reported disease status. This information is to be collected at all follow-ups for all patients.

- hematology data (i.e., CBC results per standard of care)
- applicable concomitant medications
- further treatments, including transplant status
- transfusion information date of transfusions, transfusion frequency, units, type (red blood cells, platelets), and reason for transfusion
- date of disease progression (if applicable)

• death (if applicable) - appropriately redacted documentation should be collected for source document verification (i.e. a redacted death certificate)

#### Safety Follow-up

Ongoing AEs at the time of study drug discontinuation will be followed until either 28 days after last administration of study drug or until the start of a subsequent systemic anticancer therapy, if earlier. SAEs will be followed to resolution or stabilization (see Section 7.11.4).

# 9 PLANNED STATISTICAL METHODS

Summary statistics will consist of absolute and relative frequencies of each category of discrete variables as well as of means, standard deviations, medians, minimum and maximum values of continuous variables. These summaries will be applied by dose cohort and by dose schedule in each phase of the study. Statistical methods will be applied primarily to the expansion cohorts. AML and MDS patients will be summarized together for safety and the AML efficacy population separately for efficacy analysis.

## 9.1 Determination of Sample Size for Primary Efficacy Analysis

The planned sample size for the pivotal portion of the study under Protocol Amendment 11 onwards is 170 patients, based on a three-stage design.

To determine the sample size under Amendment 11 inclusion criteria, historical reference response rates to standard treatments were ascertained through a meta-analysis based on 5 published studies that included PIF/ER AML patients selected from 963 publications identified through database search (11,12,13,30,36). Based on this analysis, the estimated combined CR/CRh rate was 11.8%, with a 95% confidence interval of 9.4% to 14.7%. The upper 95% CI of 14.7% was chosen as the rate for the null hypothesis (H0) and a target of 23% CR/CRh was established as a clinically meaningful endpoint in this patient population.

A three-stage design with two interim analyses will be employed to test the null hypothesis (H0) of CR/CRh rate = 14.7% against the alternative hypothesis (H1) of CR/CRh rate = 23%. Demonstration of CR/CRh rate improvement (H1) by rejecting H0 at a 1-sided type I error of 0.025 with adequate power (80%) in a sequential design requires 170 patients. Specifically, the planned number of patients and the futility and efficacy boundaries at each stage are as follows:

- a. **First interim analysis:** The first interim analysis will be performed after 40 patients have been enrolled and either have had their responses evaluated or were discontinued for any reason from study treatment prior to their first response assessments. This interim analysis is for futility only, that is, the study enrollment will continue if at least 5 (12.5%) out of 40 patients have response of CR/CRh.
- b. **Second interim analysis:** If the enrollment continues after the first interim analysis, a second interim analysis will be performed after additional 60 patients have been enrolled (100 patients in total) and either have had their response evaluated or were discontinued for any reason from study treatment prior to their first response assessment. This interim analysis is for both futility and efficacy. Specifically,
  - i. If the number of CR/CRh is less than 15 (15%) out of 100 patients, then the study is considered futile and enrollment will be stopped.
  - ii. If the number of CR/CRh is 15 (15%) or greater out of 100 patients, then enrollment will continue.

- iii. If the number of CR/CRh is 25 (25%) or greater out of 100 patients, then H0 is rejected and the study is considered positive. The enrollment will still continue.
- c. **Final Analysis:** If enrollment continues after the second interim, then the final analysis will be performed after additional 70 patients have been enrolled (170 patients in total) and either have had their response evaluated or were discontinued for any reason from study treatment prior to their first response assessments. If the number of CR/CRh is at least 35 (20.6%) out of the total of 170 patients, then H0 is rejected and the study is considered positive.

The above design yields a 1-sided alpha of 0.005 for the efficacy boundary at the second interim analysis and an overall 1-sided alpha of 0.024 with approximately 80% power at the final analysis. The probability of early termination under H0 (futility) in the first two stages is 55%.

# 9.2 Analysis Populations

Three populations will be used for analysis, as defined below:

- Efficacy population All patients that have been enrolled under Protocol Amendment 11 or later and treated with flotetuzumab at the MTD of 500 ng/kg/day as a continuous 7-day per week IV infusion during Cycle 1, have received any portion of one dose of flotetuzumab, and met the definition of PIF/ER AML based on inclusion criteria as revised in Amendment 11 (see Section 5.1). This population will be used for the primary analysis of efficacy endpoints.
- Safety population All patients who received any portion of any dose of flotetuzumab. AML and MDS will be analyzed as pooled and separate populations for safety and PK. The analysis of all safety endpoints will be based on the safety population.
- **Response evaluable population** All patients in the efficacy population that have a baseline bone marrow assessment, have at least one post-infusion assessment of their disease status or were removed from the study for reason of documented evidence of disease progression, death or treatment-related adverse event. This population will be used in the summary of response rate as a secondary analysis.

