#### **Analysis Populations:**

Three populations will be used for analysis, as defined below:

- Efficacy population All patients that have been enrolled under Protocol Amendment 11 or later and treated with flotetuzumab at the MTD of 500 ng/kg/day as a continuous 7-day per week IV infusion during Cycle 1, have received any portion of one dose of flotetuzumab, and met the definition of PIF/ER AML based on inclusion criteria as revised in Amendment 11 (see Section 5.1). This population will be used for the primary analysis of efficacy endpoints.
- Safety population All patients who received any portion of any dose of flotetuzumab. AML and MDS will be analyzed as pooled and separate populations for safety and PK. The analysis of all safety endpoints will be based on the safety population.
- **Response evaluable population** All patients in the efficacy population that have a baseline bone marrow assessment, have at least one post-infusion assessment of their disease status or were removed from the study for reason of documented evidence of disease progression, death or treatment-related adverse event. This population will be used in the summary of response rate as a secondary analysis.

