## 4.1.1 Cohort Expansion Dosing

The highest incidence and severity of IRR/CRS is usually noted in the first week of dosing, with peak incidence around 48 to 72 hours post start of dosing; IRR/CRS was not typically observed beyond the first week of administration. In view of this, patients who experienced Grade 1 or 2 IRR/CRS that required minimal intervention, i.e., only anti-pyretics or antihistamines and after consultation between the treating Investigator and the Sponsor, may receive flotetuzumab as outpatients after Cycle 1 Day 8 (and after a minimum of 24 hours at the 500 ng/kg/day maximum dose). Following a dosing interruption for > 24 hours for any reason, patients are required to be hospitalized for the first 24-48 hours of dose re-initiation for observation and management of IRR/CRS. Once no IRR/CRS  $\geq$  Grade 2 is observed in a given patient, and they have otherwise demonstrated acceptable tolerability of the flotetuzumab regimen in the judgment of the Investigator, they may be considered for outpatient treatment without hospitalization for observation.

Flotetuzumab will be dosed using a multi-step lead-in dose approach for intrapatient dose escalation using multiple-step increments in dosing as follows: 30, 60, 100, 200, 300, 400 ng/kg/day each for 24 hours ( $\pm$  2 hours). On Day 7, the dose will be increased to 500 ng/kg/day and administered as a continuous infusion for the remainder of Cycle 1 (Table 2). Cycle 1 Week 2 and beyond will follow the Table 2 dosing schedule.

Patients that have a dosing interruption > 72 hours will reinitiate dosing with a modified multi-step lead-in dose starting at 30 ng/kg/day (followed by steps up to 60, 100, 200, 300, 400, and 500 ng/kg/day) with dose changes every 4-6 hours as tolerated.

Cycle	Week	Days	ng/kg/day
			Induction
		Day 1	30
		Day 2	60
1		Day 3	100
	Day 4	200	
1		Day 5	300
1		Day 6	400
		Day 7	500
	2	Days 8-14	500
	3 4	Days 15-21	500
		Days 22-28	500
		Additional Indu	iction Cycles, if appropriate
	1	Days 1 – 7	500
up to 5	2	Days 8 – 14	500
cycles	3	Days 15 – 21	500
	4	Days 22 – 28	500
		Additional Consol	lidation Cycles, if appropriate
	1	Days 1 – 7	500
up to 2	2	Days 8 – 14	500
cycles	3	Days 15 – 21	500
	4	Days 22 – 28	500

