#### Table 5CRS Grading and Recommended Management Guidance

CRS Grade (26)	Dose Modification	Tocilizumab	Corticosteroids
Grade 1 Symptoms are not life threatening and require symptomatic treatment only, e.g., fever, nausea, fatigue, headache, myalgias, malaise	Slow infusion rate by 10-20%. After stabilization/resolution increase infusion rate as clinically indicated every 4-6 hours.	Administer tocilizumab (14) 8 mg/kg IV over 1 hour (not to exceed 800 mg/dose). If no clinical improvement in the signs and symptoms of CRS after the first dose, repeat tocilizumab every 8 hours as needed. Limit to a maximum of 3 doses in a 24-hour period; maximum total of 4 doses.	Administer dexamethasone (e.g., 4 to 6 mg IV or oral every 8 hours) for 24-48 hours.
Grade 2 Symptoms require and respond to moderate intervention Oxygen requirement < 40% or Hypotension responsive to fluids or low-dose of one vasopressor (Table 6) or Grade 2 organ toxicity	Slow infusion rate by 25-50%. After stabilization/resolution increase infusion rate as clinically indicated every 4-6 hours.	Per Grade 1	Manage per Grade 3 if no improvement or worsening within 24 hours after starting tocilizumab.
Grade 3 Symptoms require and respond to aggressive intervention Oxygen requirement ≥ 40% or Hypotension requiring high-dose vasopressors or multiple vasopressors (Table 6) or Grade 3 organ toxicity (except transaminitis) or Grade 4 transaminitis	Interrupt infusion, DO NOT FLUSH line. Aspirate residual drug from line. After resolution or stabilization to Grade 1 resume infusion at previous tolerated dose, and increase rate as clinically indicated every 4-6 hours.	Per Grade 1	Administer dexamethasone (e.g., 8 to 10 mg intravenously every 8 hours) or equivalent. Continue corticosteroid use until the event is Grade 1 or less, then taper over 3 days.

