1 For patients who will discontinue therapy, a PK sample is to be collected at end of infusion. When dosing is delayed for ≥ 24 hours, PK samples should not be collected on days when no study drug is administered. After Cycle 1 Day 1, PK samples do not need to be collected if patient does not reach 500 ng/kg/day dose level.

2 Sample may be drawn up to Day -5.

3 Cycle 1 Day 29 PK samples are only to be collected if there is a > 24 hour interruption in treatment between Cycles 1 and 2.

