5 STUDY POPULATIONS

Three populations will be used for analysis, the efficacy population, safety population and the evaluable population, as defined below:

- Efficacy population All patients that have been enrolled under protocol amendment 11 or later and treated with flotetuzumab at the MTD of 500 ng/kg/day as a continuous 7-day per week IV infusion during Cycle 1, have received any portion of one dose of flotetuzumab, and met the definition of PIF/ER AML based on Amendment 11 inclusion criteria . This population will be used for the primary analysis of efficacy endpoints.
- Safety population All patients who received any portion of any dose of flotetuzumab. AML and MDS will be analyzed as pooled and separate populations for safety and PK. The analysis of all safety endpoints will be based on the safety population.
- **Response evaluable population** All patients in the efficacy population that have a baseline bone marrow assessment, have at least one post-infusion assessment of their disease status or were removed from the study for reason of documented evidence of disease progression, death, or treatment-related adverse event. This population will be used in the summary of response rate as a secondary analysis.

Patients who die before having a post-infusion disease assessment will be considered evaluable for OS and EFS analyses.

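### The protocol gives two different enrolment windows for the 170-patient primary efficacy set (Section 2.3.2.3 against Section 9.2), and the dose condition in the definition needs a clarifying phrase

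*Protocol*

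**What the plan says.** Three places define the efficacy population in nearly the same words: the synopsis, Protocol 9.2 and SAP 5. Each joins these conditions:

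- The patient was "enrolled under Protocol Amendment 11 or later and treated with flotetuzumab at the MTD of 500 ng/kg/day". Protocol 9.2 continues the dose condition as "treated with flotetuzumab at the MTD of 500 ng/kg/day as a continuous 7-day per week IV infusion during Cycle 1".
- The patient must also "have received any portion of one dose of flotetuzumab".
- The patient meets the PIF/ER definition of Amendment 11.

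Protocol 9.1 and SAP 4.2 plan 170 patients for the pivotal portion, starting with Amendment 11.

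Protocol 2.3.2.3, under its Primary Efficacy Analysis subheading, also gives 170 as the sample size. It says the analysis takes in every patient treated at 500 ng/kg/day by continuous infusion in Cycle 1 who meets the Amendment 11 PIF/ER definition, with no restriction on enrolment date and with either the two-step or the multi-step lead-in.

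On dosing, Section 4.1.1 states: "On Day 7, the dose will be increased to 500 ng/kg/day". Lower doses are given on Days 1 to 6. Appendix 2 foresees patients who never get there: "PK samples do not need to be collected if patient does not reach 500 ng/kg/day dose level". For Grade 3 CRS, Table 5 has the site interrupt and later "resume infusion at previous tolerated dose, and increase rate as clinically indicated every 4-6 hours".

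On counting, each analysis in Section 9.1 includes enrolled patients who were evaluated or who "were discontinued for any reason from study treatment prior to their first response assessments". The final rule is a count: "If the number of CR/CRh is at least 35 (20.6%) out of the total of 170 patients".

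**The concern.** This set is the denominator of a single-arm, open-label comparison with a fixed 14.7%, on a response that investigators assess. Which patients belong to it should not be open to choice once data exist.

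The enrolment window matters most. Section 2.3.2.3 itself reports that response data from the first 24 patients enrolled under Amendment 7 guided the restriction of enrolment to PIF and ER patients. If earlier patients also count in the pivotal 170, data that shaped the target population are reused to test the hypothesis in that population.

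The dose condition matters less. Read word for word, it makes membership depend on tolerating the step-up to 500 ng/kg/day. That would remove mainly early stoppers after treatment had begun and raise the rate without any drug effect.

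**Working it through.** **1. Enrolment window, side by side.**

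| Place | Who enters the primary set |
|---|---|
| Protocol 2.3.2.3 | Any enrolment date; two-step or multi-step lead-in |
| Synopsis, Protocol 9.2, SAP 5 | Amendment 11 or later |
| Protocol 9.1, SAP 4.2 | 170 planned from Amendment 11 onward |

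The wider window is not just loose phrasing. Section 2.3.2.3 says the multi-step lead-in replaced the two-step lead-in as of Amendment 8. Allowing either lead-in therefore has an effect only for patients enrolled before then. Under the Section 9.2 window that allowance is empty.

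The documents do not say how many earlier patients would qualify. Section 4.1 expects about 271 expansion patients at 500 ng/kg/day, and 271 − 170 = 101 would lie outside a pivotal set of 170. This is not a count of those affected: many of these patients may fail the Amendment 11 PIF/ER definition, and some patients in the dose-escalation segment might meet it.

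**2. The plan's own operating characteristics.** Inputs from Protocol 9.1: stage sizes 40, 60 and 70; continue at ≥5/40 and ≥15/100; success at ≥25/100 or ≥35/170; null rate 0.147 and target rate 0.23. With X1 ~ Bin(40, p), X2 ~ Bin(60, p), X3 ~ Bin(70, p) and S2 = X1 + X2, the exact sums are:

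- Early stop under the null: P(X1 < 5) + P(X1 ≥ 5, S2 < 15) = 0.2806 + 0.2654 = 0.546 (stated 55%).
- Success at the second look: P(X1 ≥ 5, S2 ≥ 25) = 0.0047 (stated 0.005).
- Success at the final look: P(X1 ≥ 5, 15 ≤ S2 < 25, S2 + X3 ≥ 35) = 0.0192.
- Overall alpha: 0.0047 + 0.0192 = 0.0239 (stated 0.024).
- Power at 0.23: 0.787 (stated about 80%).

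The stated figures are reproduced.

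**3. Literal dose condition, with boundaries applied to 170 treated patients.** Suppose k treated patients never reach 500 ng/kg/day and none responds; both are assumptions. The test still uses counts out of 170, so alpha stays 0.0239. The reported rate becomes r/(170 − k), with exact lower limit L = Beta⁻¹(0.025; r, n − r + 1) for n = 170 − k.

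| Responders/n | Rate | Exact 95% limits |
|---|---|---|
| 35/170 (just passes) | 20.6% | 14.78% to 27.45% |
| 34/170 (fails) | 20.0% | 14.27% to 26.81% |
| 34/166 (k = 4) | 20.5% | 14.62% to 27.43% |
| 34/165 (k = 5) | 20.6% | 14.71% to 27.59% |
| 34/162 (k = 8) | 21.0% | 14.99% to 28.07% |

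Five exclusions are the fewest that lift the lower limit for 34 responders above 14.7%. The report could then seem to contradict a failed test.

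**4. What it would take for alpha to exceed 0.025.**

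- *Filling the 170 from the restricted set.* With a share f excluded, all non-responders, the apparent null rate is 0.147/(1 − f). For f = 1/171, 3%, 5% and 10% this is 0.1479, 0.1515, 0.1547 and 0.1633, and alpha is 0.0258, 0.0353, 0.0456 and 0.0845.
- *Applying the second-look boundary as a 25% rate to a reduced denominator.* With 3, 5 or 10 of the 100 excluded, the thresholds are 25/97, 24/95 and 23/90, and overall alpha is 0.0239, 0.0264 and 0.0320.

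The shares are assumptions; the documents give none. If some excluded patients respond, the effect is smaller. If they respond at the same rate as the others, there is none.

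**The case against.** On the window, the case is that Section 2.3.2.3 sits in the background chapter, in a summary of prior development, and that all the operative statistical text points to Amendment 11 onward. That is fair, and the operative text would probably prevail. But the passage is current, is written in the future tense, carries the primary analysis as its subheading and states the same 170. A protocol should not contain two versions.

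On the dose condition, a reader might infer that the plan excludes everyone who stops in the lead-in. The documents do not support that:

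- Taken strictly, a whole Cycle 1 at 500 ng/kg/day fits no patient on the lead-in schedule, so the phrase works better as the name of a regimen.
- Section 2.3.2.3 uses almost the same phrase and disregards the type of lead-in.
- Section 4.1 describes patients still to be enrolled as treated at that dose.
- The any-portion clause would have no function under the literal reading.
- Section 9.1 counts patients who discontinued before any assessment.
- A narrower response-evaluable set already exists and serves only as a sensitivity analysis.
- The Appendix 2 footnote concerns PK sampling and says nothing about who is analysed.

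Most of this objection stands. What remains is that no sentence states the regimen reading, and the SAP repeats the wording instead of settling it.

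**Conclusion.** The contradiction over the enrolment window is definite and should be corrected. Its numerical effect cannot be computed, because the number of earlier patients who would qualify, and their responses, are not given.

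The dose condition is a drafting ambiguity. If it were applied literally to non-responders, the reported rate and interval would be too favourable by the amounts in step 3. The size rests on an assumed number of exclusions and on zero response among them.

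A reader might also infer that type I error is inflated. The documents do not support that. It would require filling the 170 from the restricted set, which Section 9.1 does not suggest, or treating the 25% in Section 9.6.1 as a rate on a smaller denominator. The latter is strained, since Section 9.1 and SAP 13.4 give that boundary as 25 of 100.

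The definition also does not name the ruxolitinib mini-cohort of up to 12 patients, which Section 4.1 lists separately as exploratory. The number who would qualify may be zero, and no effect is shown.

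**What to change.** - Bring Protocol 2.3.2.3 into line with the Amendment 11-or-later definition.
- In the synopsis, Protocol 9.2 and SAP 5, define the efficacy population as all patients enrolled under Amendment 11 or later to the 500 ng/kg/day continuous-infusion regimen, outside the ruxolitinib mini-cohort, who meet the Amendment 11 PIF/ER definition and received any portion of any dose, whether or not 500 ng/kg/day was reached.
- State that patients without a response assessment count as non-responders, as Sections 9.1 and 9.6.1 already imply.
- Use this one set for the 40, 100 and 170 counts, the boundaries, and the reported rate and confidence interval.
- As minor clarifications, state the second-look boundary as 25 of 100 in the synopsis, Protocol 9.6.1 and SAP 11.1, and report ruxolitinib patients separately.

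The cost is protocol and SAP wording, with no new data. The reported rate may be slightly lower than under the literal reading.
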